## 6.2.3. Analysis of safety

Not applicable since no subject intervention is involved in this exploratory study concerning retrospective laboratory analyses of archived serum samples.

# 7. STATISTICAL CALCULATIONS

## 7.1. Derived and transformed variables

- Immunogenicity
  - For a given subject and given immunogenicity measurement, missing or non-evaluable measurements will not be replaced. Therefore, an analysis will exclude subjects with missing or non-evaluable measurements
  - The cut-off value is defined by the laboratory before the analysis and is described in Section 5.4.1 (Table 2) of the protocol.
  - A seronegative subject is a subject whose titer is below the cut-off value.
  - A seropositive subject is a subject whose titer is greater than or equal to the cut-off value.
  - The Geometric Mean Titers (GMTs) calculations are performed by taking the anti-log of the mean of the log titer transformations. Antibody titers below the cut-off

# Statistical Analysis Plan

Study alias & e-track number(s): Flu CC-SUIV-AS03-001 (201598)

of the assay will be given an arbitrary value of half the cut-off for the purpose of GMT calculation.

- The 95% CI for geometric mean titres (GMTs) will be obtained within each group separately. The 95% CI for the mean of log-transformed titre will be first obtained assuming that log-transformed values were normally distributed with unknown variance. The 95% CI for the GMTs will be then obtained by exponential-transformation of the 95% CI for the mean of log-transformed titre.
- Four-fold antibody titer increase is defined as post/pre for seropositive subjects; and post/half of the cut off value for seronegative subjects
- *Ten-fold antibody titer increase is defined as post/pre for seropositive subjects; and post/half of the cut off value for seronegative subjects*
- All CI computed will be two-sided 95% CI. The exact 95% CIs for a proportion within a group will be based on the method by Clopper [Clopper, 1934\*].

## 8. CONDUCT OF ANALYSES

The planned analysis is descriptive and will be performed for each treatment group in the individual study **cohort**. No pooled analysis will be performed.

Any deviation(s) or change(s) from the original statistical plan outlined in the protocol will be described and justified in the final study report.

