# Statistical Analysis Plan

Study alias & e-track number(s): Flu CC-SUIV-AS03-001 (201598)

vaccinated with 2 doses of adjuvanted (AS03B) Q-PAN H5N1 vaccine (half adult dose, i.e., 1.9 µg) *or with placebo*. This will allow an evaluation of the vaccine's potential to elicit anti-H1 HA stalk reactive antibodies in those children who were anti-H1N1 HI negative at baseline (i.e., in the absence of priming due to prior exposure to H1N1). For this pediatric H5N1 cohort, samples will be analyzed from 4 timepoints (D0, D21, D42, and D385) collected from approximately 30 subjects from the adjuvanted vaccine treatment group *and 30 subjects from the placebo group*.

*In addition, serum samples from the adults subjects 18 to 40 years of age enrolled in group C and G of the Q-Pan-005 study will be used to describe the anti HA stalk response following a heterologous booster dose of an adjuvanted pandemic vaccine (i.e. an adjuvanted monovalent A/turkey/Turkey/1/05 (H5N1) vaccine) administered to subjects primed 18 months earlier with an adjuvanted monovalent A/Indonesia/5/05 (H5N1) vaccine. The anti HA stalk response after an homologous booster dose of the adjuvanted monovalent A/turkey/Turkey/1/05 (H5N1) vaccine administered to subjects primed with the same vaccine 12 months earlier will also be described. Samples from the H5N1-012 study will also be used to measure the antibodies directed against the H1 HA stalk domain elicited by an adjuvanted H5N1 vaccine booster dose (A/Vietnam/1194/2004 like or A/Indonesia/5/2005 like) administered 12 months after an homologous or an heterologous adjuvanted priming dose (A/Vietnam/1194/2004) in subjects 18-60 years of age. The analysis will be stratified by age (18-30 years vs 31-60 years) to evaluate the age effect on the immune response. These assessment will be informative for designing the E-SUIV-001 Phase 1 study in which the vaccine schedules are planned to be similar to the ones of the Q-Pan-H5N1-005 and the H5N1-012 study.*

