# Statistical Analysis Plan

Study alias & e-track number(s): Flu CC-SUIV-AS03-001 (201598)

		AS03 A vaccine at D0 and D21 in H5N1-001 study
4	H5N1_NAS	CC-PAN H5N1 (A/Indonesia/5/2005 RG) 15 µg vaccine at D0 and D21 in H5N1-001 study
5	H9N2_AS	Q-Pan H9N2 (A/chicken/Hong Kong/G9/1997 NIBRG-91) 3.75 µg + AS03 A vaccine at D0 and D21 in H9N2-001 study (375_A_VVP + 375_A_VVV group)
6	H9N2_NAS	Q-Pan H9N2 (A/chicken/Hong Kong/G9/1997 NIBRG-91) 15 µg vaccine at D0 and D21 in H9N2-001 study (1500_VVP + 1500_VVV group)
7	H5N1_PAS	Q-PAN H5N1 (A/Indonesia/5/2005 RG) 1.90 µg + AS03 B vaccine at D0 and D21 in pediatric Q-PAN-H5N1-AS03-021 study
8	H5N1_PCN	Placebo at D0 and D21 in pediatric Q-PAN-H5N1-AS03-021 study
9	H7N9_AS	Q-PAN H7N9 (A/Shanghai/2/2013(H7N9)-RG32A)3.75 µg + AS03A vaccine at D0 and D21 in Q-PAN-H7N9-AS03-001 study
10	H7N9_NAS	Q-PAN H7N9 (A/Shanghai/2/2013(H7N9)-RG32A)15 µg vaccine at D0 and D21 in Q-PAN-H7N9-AS03-001 study
11	DQIV_NAS	Seasonal 15 µg vaccine at D0 in D-QIV-015 study
12	QPAN5_C	Q-PAN H5N1 (A/Indonesia/5/05) 3.8 µg + AS03A on D0, placebo on Day 182; (A/turkey/Turkey/1/05) 3.8 µg + AS03A on Day 549 in Q-Pan-005 study
13	QPAN5_G	Placebo on Day 0, 3.8 µg A/turkey/Turkey/1/05 (H5N1) with AS03A on Days 182 and 549 in Q-Pan-005 study
14	H5N1_VT	Adjuvanted (AS03A) pandemic Vietnam strain influenza vaccine at Day 0 and Month 12 in H5N1-012 study
15	H5N1_IN	Adjuvanted (AS03A) pandemic Vietnam strain at Day 0 and adjuvanted (AS03A) pandemic Indonesia influenza strain at Month 12 in H5N1-012 study

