# Statistical Analysis Plan

Study alias & e-track number(s): Flu CC-SUIV-AS03-001 (201598)

- Geometric mean titer (GMT) at Day 0, 21, 42 and at Day 385
- Percentage of subjects with a  $\geq 4$ -fold rise from Day 0 to Day 21 ***and from Day 0 to Day 42***
- ***Percentage of subjects with a  $\geq 10$ -fold rise from Day 0 to Day 21 and from Day 0 to Day 42***
- Mean geometric increase (MGI) at Day 21, 42 and at Day 385 compared to Day 0
- ***For adult subject samples from the Q-Pan-005 study cohort, groups C and G:***
  - ***Seropositive rate at Day 0, 42, 182, 224, 549, 591, and at Day 729***
  - ***Geometric mean titer (GMT) at Day 0, 42, 182, 224, 549, 591, and at Day 729***
  - ***Percentage of subjects with a  $\geq 4$ -fold rise***
    - ***For group C: From Day 0 to Day 42, from Day 549 to Day 591 and from Day 0 to Day 591***
    - ***For group G: From Day 182 to Day 224, from Day 549 to Day 591 and from Day 182 to Day 591***
  - ***Percentage of subjects with a  $\geq 10$ -fold rise***
    - ***For group C: From Day 0 to Day 42, from Day 549 to Day 591 and from Day 0 to Day 591***
    - ***For group G: From Day 182 to Day 224, from Day 549 to Day 591 and from Day 182 to Day 591***
  - ***Mean geometric increase (MGI) at Day 42, 182, 224, 549, 591, and at Day 729 compared to Day 0 for group C and for Day 224, 549, 591 and Day 791 compared to Day 182 for group G***
- ***For adult subject samples from the H5N1-012 study cohort (groups VT/VT/12M and VT/IN/12M):***
  - ***Seropositivity rate at Day 0, 21, M6, M12, M12+21days and M18***
  - ***GMT at Day 0, 21, M6, M12, M12+21days, and M18***
  - ***Percentage of subjects with a  $\geq 4$ -fold rise from Day 0 to Day 21, from M12 to M12+21days, and from Day 0 to M12+21days***
  - ***Percentage of subjects with a  $\geq 10$ -fold rise from Day 0 to Day 21, from M12 to M12+21days, and from Day 0 to M12+21days***
  - ***MGI at Day 0, 21, M6, M12, M12+21, and M18***
- ***For adult subject samples from the FLUD-QIV-015 study cohort:***

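### H5N1-012: both groups share one priming regimen until Month 12, but only by-group estimates are planned, so priming intervals are about 1.4 times as wide as a combined estimate would give

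*SAP*

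**What the plan says.** The group table in section 2 of the SAP defines group 14 (H5N1_VT) as adjuvanted "pandemic Vietnam strain influenza vaccine at Day 0 and Month 12 in H5N1-012 study". Group 15 (H5N1_IN) gets the adjuvanted Vietnam strain at Day 0 and then the adjuvanted "pandemic Indonesia influenza strain at Month 12 in H5N1-012 study". Table 1 in the same section takes all available subjects, about 60 in each group.

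Section 4.1 lists the H5N1-012 outputs among the primary endpoints. For anti-H1 stalk ELISA it includes "GMT at Day 0, 21, M6, M12, M12+21days, and M18", and seropositivity, MGI and fold rises are set out in the same way. Section 2 adds, for this cohort, "The analysis will be stratified by age (18-30 years vs 31-60 years", closing the bracket there, in order to look at an effect of age and to inform the next study.

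Three places make the results by-group only. Section 6.2.1 works through each study group. Section 7.1 says: "The 95% CI for geometric mean titres (GMTs) will be obtained within each group separately". Section 8 says: "The planned analysis is descriptive and will be performed for each treatment group in the individual study" cohort, and then: "No pooled analysis will be performed".

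**The concern.** Up to and including Month 12 the two groups have had the same strain, adjuvant and day of vaccination. Results at Day 0, Day 21, Month 6 and Month 12, and the rises from Day 0 to Day 21, describe the response to one regimen. The plan gives that response twice, each time from half of the available subjects, and never once from all of them.

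The study is descriptive, so the width of its intervals is what it delivers. The H5N1-012 results are meant to help design a further study with a similar schedule, and the age stratification divides each group again. Two values for one regimen also invite a reader to interpret a gap between them that the treatments cannot explain before Month 12.

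**Working it through.** The SAP gives no sample-size or precision figure for H5N1-012, so there is none to reproduce. The check applies the SAP's own interval rules at the by-group and the combined sample size.

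**Inputs**
- n: about 60 per group (Table 1), so about 120 combined.
- GMT interval: t-based on log titres (section 7.1). I assume the same method for MGI, which 7.1 does not spell out.
- Proportions: two-sided 95% Clopper-Pearson (section 7.1).
- Assumed, because the SAP gives neither: log10 SD between 0.3 and 0.6, and 20 to 30 subjects per group in an age stratum.

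**Step 1, standard error.** SE = SD/√n. The ratio by-group to combined is √(120/60) = 1.414. The reduction from combining is 1 − 1/1.414 = 0.29.

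**Step 2, GMT and MGI.** Half-width = t(0.975, n−1) × SD/√n.
- n = 60: 2.001/7.746 = 0.2583 SD
- n = 120: 1.980/10.954 = 0.1808 SD
- Ratio: 0.2583/0.1808 = 1.43. The SD cancels, and the ratio is still 1.43 with 50 or 55 evaluable subjects per group.

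As fold factors around the GMT (10 to the power of the half-width):

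| log10 SD (assumed) | n = 60 | n = 120 |
|---|---|---|
| 0.3 | 1.20 | 1.13 |
| 0.4 | 1.27 | 1.18 |
| 0.5 | 1.35 | 1.23 |
| 0.6 | 1.43 | 1.28 |

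**Step 3, proportions.**

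| Observed rate | 95% CI, n = 60 | 95% CI, n = 120 | Width ratio |
|---|---|---|---|
| 0% | 0–6.0% | 0–3.0% | 1.97 |
| 5% | 1.0–13.9% | 1.9–10.6% | 1.48 |
| 10% | 3.8–20.5% | 5.3–16.8% | 1.45 |
| 50% | 36.8–63.2% | 40.7–59.3% | 1.42 |

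Rates of 90%, 95% and 100% mirror those of 10%, 5% and 0%.

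**Step 4, age strata.** The t-based ratio is 1.45 for 30 against 60 subjects and 1.46 for 20 against 40. At a 50% rate, 30 subjects give 31.3–68.7% and 60 give 36.8–63.2%.

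**Step 5, what can be combined without new testing** (section 4.1).

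| Assay | Pre-booster time points | Rises, Day 0 to Day 21 |
|---|---|---|
| Anti-H1 stalk ELISA | Day 0, 21, M6, M12 | 4-fold and 10-fold |
| Anti-H1 stalk MN | Day 0, 21, M6, M12 | 4-fold and 10-fold |
| Anti-H2 and anti-H18 ELISA | Day 0, 21, M12 | 4-fold |
| Heterosubtypic MN | Day 0, 21, M12 | 4-fold |

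For heterosubtypic MN the seropositivity line prints M1 where the GMT and MGI lines, and section 3.1, have M12. I have read it as M12.

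**The case against.** The strongest reply is that nothing here is wrong. Separate description of each treatment group is a normal convention, and no hypothesis, power claim or decision threshold depends on H5N1-012. Each group's own Day 0 and Month 12 values are needed as the reference for its booster response. That stands. It rules out replacing the by-group results, but not adding a combined one.

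The section 8 sentence may also have been aimed only at pooling across studies, since it follows a statement about individual study cohorts. That is plausible. Even so, the group definitions and sections 6.2.1 and 7.1 lead to by-group results alone.

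A reader might infer that the SAP contradicts itself, because it merges two H9N2 sub-groups: "vaccine at D0 and D21 in H9N2-001 study (375_A_VVP + 375_A_VVV group", and likewise for the unadjuvanted arm. The documents do not support that. Those sub-groups differ only by what is given at Day 182, which is the last sampled day for H9N2, whereas the H5N1-012 groups diverge within their sampled period. The H9N2 handling shows that the SAP accepts combining subjects treated alike, and no more.

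A reader might also infer that any pre-booster difference between the groups must be chance. This too goes further than the text. The statement that the primary studies were randomised is general. The subjects come from according-to-protocol cohorts whose numbers vary by time point, so exclusions after allocation could differ between groups by Month 6 or 12.

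Finally, a reader could rebuild a combined value from the by-group tables by adding counts and weighting log GMTs by n. This limits the harm, but leaves the combination to be done after the results are known.

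**Conclusion.** The point holds as avoidable imprecision, not as bias, an error-rate problem or an internal contradiction. Intervals for the common priming response and its persistence to Month 12 are about 1.4 times as wide as a combined estimate would give. For exact intervals at 0% or 100% the ratio is close to 2. In absolute terms the gain in GMT precision is modest, for example a factor of 1.27 reduced to 1.18 at an assumed SD of 0.4. It is worth most in the age strata.

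The ratio rests on roughly equal groups of about 60 and depends on no assumed SD. It also rests on the priming doses being the same: the SAP gives strain, adjuvant and day for H5N1-012 but no HA content. The absolute widths and the stratum figures rest on the assumed ranges stated with them. This is a worthwhile, inexpensive improvement; the analysis would remain valid without it.

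**What to change.** - **Add** a combined VT/VT/12M + VT/IN/12M priming estimate to the H5N1-012 items in section 4.1 and to section 6.2.1. Give it overall and for ages 18-30 and 31-60, at the time points and rises in the last table of the working, and nowhere else.
- **Keep** the by-group results at all time points, because the pre-booster values are the reference for each booster response. Report M12+21 days, M18 and every rise that spans the booster by group only.
- **Reword** section 8 along these lines: *No pooling across study cohorts will be performed. The two H5N1-012 groups are also combined for the pre-booster time points.*
- **State** beside the combined estimate how many subjects each group contributes at each time point, since the according-to-protocol numbers vary.

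The cost is a few extra table columns per assay (overall and two strata), with no new samples or assays. The two table templates listed at the front of the SAP do not cover H5N1-012, so the columns can be built in when that template is written, before results are seen.

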### 8.1. Sequence of analyses

*Analyses will be performed in sequence based on availability of the different results.*  
Results will be presented in a final study report.

### 8.2. Statistical considerations for interim analyses

Not applicable since no interim analyses are planned; *all analyses will be descriptive*

## 9. CHANGES FROM PLANNED ANALYSES

Not applicable

## 10. REFERENCES

SAS software will be used to derive the confidence intervals

